5.5.3 Magnetic Resonance Imaging

Cranial MRI will be performed as follows; the data will be collected in the eCRF as described below:

	■	■	■	■	■
Number of contrasts enhancing lesions (CEL)	x	x	x		
Number of new/enlarging T2 lesions*		x	x	x	x
Total number of T2 lesions	x				

* New/enlarging T2 lesions are calculated in reference to the previous MRI

Cranial MRI scans without contrast agent can also be performed during unscheduled visits. The number of new/ enlarging T2 lesions observed during unscheduled visit will be documented in the eCRF.

The number of CELs, total or new/ enlarged T2 lesions collected during the scheduled visits will be summarized. All collected data will be listed.

Baseline will be defined as the number of CELs at Visit 1.

Lesion size data will be available from MRI images and will be summarized by visit, dose group, and overall.

When combining the eCRF-based MRI data and the MRI data provided by Jung Diagnostics GmbH (JungD), the following rules will be applied:

- Data collected during an unscheduled visit after a scheduled visit with planned MRI assessments where MRI was not performed will be assigned to that scheduled visit.
- Gad+ lesion data available in the JungD data set will not be used if it is collected during a visit where contrast enhancing lesion (CEL) data collection is not planned.
- Gad+ lesion data available in the JungD data set where CEL data collection was planned and is not available in the eCRF due to data collection issues will be used.

The following statistical output will be presented:

Table 15.2.3 Summary of MRI Data – Modified Safety Analysis Set

The default summary statistics of number of CELs, new/ enlarging T2 and total number of T2 lesions and lesion size as well as change from baseline will be presented by dose group and overall. This summary will be performed by treatment cycle subgroup.

Listing 16.2.5 MRI Data – Enrolled Analysis Set

MRI results will be listed.

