#### 14.1.8 Unscheduled Visit

In case of symptoms that suggest a possible relapse, i.e. new neurological symptoms or worsening of previous symptoms, the following assessments will be performed during an unscheduled visit:

- Physical examination
- Vital signs
- Urinary pregnancy test in women of childbearing potential
- **Cranial MRI (without contrast)**; (can be performed  $\pm 5$  days). If the MRI will be performed before the UV urinary pregnancy test has to be performed at the site prior to the MRI
- Hematology: complete blood count with differential and platelet count, Coombs test, coagulation studies (PT, PTT, INR) and sedimentation rate
- Clinical chemistry: Sodium, potassium, creatinine, eGFR, urea, total bilirubin, GGT, ALT/GPT, AST/GOT, alkaline phosphatase, total protein, albumin, lactate dehydrogenase, fibrinogen, CRP, iron, ferritin, haptoglobin
- Urinalysis: specific gravity, pH, glucose, protein, ketones, nitrite, leukocytes and blood
- EDSS
- 9-HPT, T25-FW, SDMT

- MS relapse assessment
- Concomitant medication
- Adverse events
- In case of symptoms not related to a potential relapse, it is up to the Investigator to decide which of the abovementioned assessments should be performed during the unscheduled visit.

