2.2 Study Endpoints

2.2.1 Primary Endpoints

Safety Endpoints:

- The number and severity of treatment-emergent adverse events (TEAEs)
- The number and severity of treatment-emergent serious adverse events (TESAEs)
- The number of confirmed relapses
- The number and size of brain lesions

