2.3 Overall Study Design

Open-label, ascending-dose Phase Ib trial to evaluate the safety and tolerability of three doses of CLS12311 in patients with relapsing-remitting multiple sclerosis (RRMS).

The study will be conducted at approximately 12 sites in Europe.

The total duration will be at least 48 weeks for each participant and will include a total of 16 visits divided into two phases: an open-label treatment phase and a safety follow-up phase. The study phases are described in more detail in the following paragraphs.

Patient eligibility will be assessed during Visit 1 (week 0) at baseline, where general patient and disease characteristics will be recorded. Patients who meet the criteria for enrollment will be sequentially allocated to one of the dose groups. The allocation to the dose group and the timing of treatment administration will be centrally coordinated to ensure appropriate safety assessments between dosing of patients. Hence, the time-period between Visit 1 and Visit 2 might vary between patients.

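### T2 lesions first seen on a suspected-relapse MRI can drop out of the primary imaging summary, because SAP 5.5.3 summarises scheduled scans only and does not define the reference scan

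*SAP*

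**What the plan says.** SAP 2.2.1 names as a primary safety endpoint "The number and size of brain lesions". SAP 5.5.3 sets out how the number is obtained:

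- The footnote to the MRI collection table gives the reference for each count: "New/enlarging T2 lesions are calculated in reference to the previous MRI".
- For suspected-relapse and other unscheduled scans, "The number of new/ enlarging T2 lesions observed during unscheduled visit will be documented in the eCRF".
- The summary is limited to planned visits: "The number of CELs, total or new/ enlarged T2 lesions collected during the scheduled visits will be summarized". For everything else, "All collected data will be listed", which means Listing 16.2.5.
- One rule moves unscheduled data into the summary. It applies when an unscheduled scan follows a scheduled visit at which the planned MRI was not done; the data are then assigned to that scheduled visit.
- The total T2 count is marked in the first MRI column only. No cumulative count of new lesions is defined.

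SAP 4.8 applies no visit windows and uses nominal visits. Protocol 14.1.8 ("In case of symptoms that suggest a possible relapse") includes a cranial MRI without contrast in the assessments for that situation.

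**The concern.** The two rules in SAP 5.5.3 do not fit together. A count relative to the preceding scan is an increment, and increments add up to the whole only if every scan in the chain is included. The plan leaves some scans out of the summary without saying that they are also left out of the chain.

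The scans left out are not a random subset. They are triggered by symptoms that may be a relapse, so any lost lesions come from patients in whom worsening is suspected. Protocol 13.4.5 names disease exacerbation through immune activation as a risk and relies on MRI as a sensitive safety measure. The bias would run towards less apparent activity on a primary safety endpoint, in dose groups of 2, 3 and 4 patients where one patient can set the group result.

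**Working it through.** The documents give no lesion rate, expected count or power calculation, so there is no plan figure to reproduce. The check traces the counting rule through an assumed patient.

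**Inputs from the documents.** Dose groups of 2, 3 and 4, total 9 (SAP 2.3.1). Follow-up visits at Weeks 20, 24 and 48 (SAP 2.3.2). The MRI visit numbers are blacked out in SAP 5.5.3. I take them as Visits 1, 7, 13, 15 and 16, because SAP 5.5.8 lists those visits for laboratory tests and the MRI row of the schedule has the same columns marked. I take Visits 15 and 16 as Weeks 24 and 48.

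**Assumed lesions.** First appearing by Visit 7: 1; by Visit 13: 1; by Visit 15: 0; on an unscheduled MRI between Visits 15 and 16: 4; after that scan and by Visit 16: 1. Total 1 + 1 + 0 + 4 + 1 = 7. All scheduled MRIs are done, so the reassignment rule does not apply.

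**Reading A: the reference is any previous MRI (literal wording).** Visit 16 is read against the unscheduled scan and shows 1. Scheduled visits show 1 + 1 + 0 + 1 = 3 of 7, so 4/7 = 57% are missing. With u lesions on the unscheduled scan, the missing share is u/(3 + u): 1/4 = 25% for u = 1, up to 6/9 = 67% for u = 6.

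Effect on the Visit 16 group mean if every other patient has 0:

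| Group size | As planned | With the 4 lesions included |
|---|---|---|
| 2 | 1/2 = 0.50 | 5/2 = 2.50 |
| 3 | 1/3 = 0.33 | 5/3 = 1.67 |
| 4 | 1/4 = 0.25 | 5/4 = 1.25 |
| 9 | 1/9 = 0.11 | 5/9 = 0.56 |

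If lesions instead accrue evenly from Week 24 to Week 48, an unscheduled MRI at week w removes (w − 24)/24 of that interval's lesions: 25% at Week 30, 50% at Week 36, 75% at Week 42 and 22/24 = 92% at Week 46.

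**Reading B: the reference is the previous scheduled MRI.** Visit 16 is read against Visit 15 and shows 4 + 1 = 5. Scheduled visits show 1 + 1 + 0 + 5 = 7, and nothing is lost. Adding the unscheduled count on top would give 7 + 4 = 11, counting 4 lesions twice.

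**Reading B with no later scheduled MRI.** If the patient leaves after the unscheduled scan, scheduled visits show 1 + 1 + 0 = 2 of the 6 lesions seen, so 4/6 = 67% are missing. The protocol allows this: under section 14.1.9 the early-discontinuation (ED) MRI may be omitted when another MRI was done less than 2 weeks before. The relapse scan then stands in for the ED scan. The reassignment rule does not reach it, because that rule concerns an unscheduled scan after a missed scheduled MRI, whereas this one precedes the ED visit.

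**The case against.** The strongest reply is that the footnote belongs to a table of five planned MRIs, so the previous MRI may simply mean the previous planned one. Protocol 12.1.1.3 places the exact MRI definitions in an MRI Manual that is not among the documents. On that reading most of the loss disappears and a plain sum over all scans would overcount. This stands as a possibility and shapes the fix. It does not close the point: the SAP does not say so, and the case with no later scheduled MRI remains.

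It is also true that the lesions are not hidden. They are in Listing 16.2.5. Protocol 19.1.3 gives the DSMB the number of new lesions with no restriction to scheduled scans. The suspected relapse itself enters Table 15.2.2. Lesion size is summarised by visit and, if it measures total burden, later scans would carry these lesions; the SAP does not define it. These limit the consequences but do not correct Table 15.2.3.

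Two stronger inferences are tempting and not supported:

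- A reader might infer that the Gad+ rule ("Gad+ lesion data available in the JungD data set will not be used if it is collected during a visit" where contrast-enhancing lesion collection is not planned) also discards valid safety data and should go. The follow-up and unscheduled scans are planned without contrast, and an enhancing-lesion count from a non-contrast scan cannot be interpreted. Keeping such values out of the summary is defensible.
- A reader might infer, since "the time-period between Visit 1 and Visit 2 might vary between patients", that waiting time confounds lesion counts with dose group. No document gives waiting times or shows that they differ by group. Protocol 14.1.1 also lets the baseline MRI be done as late as the day of donation. Showing the interval is enough.

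**Conclusion.** The concern holds as a gap in a stated rule. Followed literally, SAP 5.5.3 omits from Table 15.2.3 any T2 lesion first seen on an unscheduled MRI, unless the preceding scheduled MRI was not performed or the lesion enlarges again later. If the reference is the previous scheduled MRI, the omission is limited to patients with no later scheduled MRI. Under either reading the direction is towards apparent safety.

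The actual size is unknown. The 25% to 67% for one patient, and the shifts in group mean, rest on assumed counts and show only that one scan can matter in groups this small. If no unscheduled MRI took place, the effect is nil. The point concerns new/enlarging T2 counts only. It does not show that lesions have in fact been lost, nor that data are withheld from the listing or the DSMB.

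**What to change.** In SAP 5.5.3, first state whether the reference for new/enlarging T2 lesions is any previous MRI or the previous scheduled MRI, in line with how the central reader works. Then:

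- **If any previous MRI:** add to Table 15.2.3, at each scheduled visit, the cumulative number of new/enlarging T2 lesions since the baseline MRI, summed over all MRIs including unscheduled and ED scans.
- **If the previous scheduled MRI:** keep the scheduled counts and add only unscheduled counts that no later scheduled MRI covers, so that no finding enters twice. Say how the ED scan is treated, since SAP 4.4 labels it separately from Visit 13.
- **In both cases:** footnote that a lesion enlarging repeatedly can be counted more than once, and show the interval in days since the reference scan.

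The counts are already in the eCRF or reader data. The cost is SAP wording, one extra row and a footnote. If the database is already locked, the SAP's introduction provides for an SAP Addendum.

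### SAP Table 15.2.3 promises a change from baseline for two T2 lesion counts that the collection schedule cannot supply, and the SAP text specifies no T2 count since baseline

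*SAP*

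**What the plan says.** SAP 2.2.1 lists "The number and size of brain lesions" among the primary safety endpoints. SAP 5.5.3 has a grid of five scheduled MRIs. CEL is marked at the first three and new/enlarging T2 at the second to fifth. "Total number of T2 lesions" is marked at the first only. A footnote to the grid adds: "New/enlarging T2 lesions are calculated in reference to the previous MRI".

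The section then fixes the baseline: "Baseline will be defined as the number of CELs at Visit 1". No baseline is named there for the T2 counts or for size. Table 15.2.3 is to present "summary statistics of number of CELs, new/ enlarging T2 and total number of T2 lesions and lesion size as well as change from baseline", with nothing that limits the change to CEL. On size the section says only: "Lesion size data will be available from MRI images and will be summarized by visit, dose group, and overall".

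SAP 4.7 has a general rule. Each variable's baseline is its own latest available value ahead of the first blood donation, and absolute change is the visit value minus that baseline. It points to Section 5 for detail. The EDSS and 9HPT sections restate this rule; the MRI section gives the CEL definition in its place.

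New/enlarging T2 counts from unscheduled scans are recorded and listed, but the summary covers scheduled visits. The one exception is an unscheduled scan that follows a scheduled visit whose planned MRI was missed; its data are assigned to that visit.

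**The concern.** Protocol 13.4.5 names exacerbation of disease through immune activation as a risk and relies on MRI as the sensitive safety measure. The natural question of the table is whether lesions have accumulated since the pre-treatment scan. For T2 lesions, the change-from-baseline rows look as if they answer it, but the collected data cannot fill them.

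A second gap follows from the footnote. Each new/enlarging count covers only the interval since the previous MRI, so no single summary row covers the period since baseline. If an unscheduled scan falls between two scheduled ones, the lesions it finds are outside the summary, and the next scheduled count starts from that scan. Protocol 14.1.8 calls for unscheduled scans when a relapse is suspected, so the patients affected are those in whom lesion activity matters most.

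**Working it through.** The documents state no sample size, power or error rate for this endpoint, and none is needed. The check is whether the change formula has both of its terms.

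**Inputs.** The grid in SAP 5.5.3, with the first scan as baseline. The column headers are redacted. The MRI row of the schedule (SAP Section 1) has the same pattern as the laboratory row, and SAP 5.5.8 gives the scheduled laboratory visits as 1, 7, 13, 15 and 16, so I take the scans to fall there. The result does not depend on this.

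| Measure | Scan 1 | Scan 2 | Scan 3 | Scan 4 | Scan 5 |
|---|---|---|---|---|---|
| CEL | yes | yes | yes | no | no |
| New/enlarging T2 | no | yes | yes | yes | yes |
| Total T2 | yes | no | no | no | no |

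**Formula (SAP 4.7).** Change at scan k = value at scan k − baseline value, for k = 2 to 5.

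**Result under each available baseline.**

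| Measure | Own first-scan value (SAP 4.7) | CEL at Visit 1 (SAP 5.5.3, literal) |
|---|---|---|
| CEL | scans 2 and 3 | scans 2 and 3 |
| New/enlarging T2 | 0 of 4 scans | 4 of 4 scans, each a T2 count minus a CEL count |
| Total T2 | 0 of 4 scans | 0 of 4 scans |

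Lesion size is not in the grid. Under 4.7 its change can be computed if size is measured at Visit 1. The lesion type and unit are not stated.

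**Vendor data.** The merging rules in 5.5.3 cover visit assignment and Gad+ lesions. They supply no later total T2 count, so the gap cannot be assumed to close from that source.

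**Unscheduled scans.** Let n2 to n5 be a patient's scheduled new/enlarging counts, and u the count at an unscheduled scan between scans 2 and 3. I assume that the previous MRI in the footnote includes unscheduled ones, since it is not restricted. Then n3 counts only from the unscheduled scan.

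- Since baseline: n2 + u + n3 + n4 + n5
- In the summary: n2, n3, n4 and n5, which add to n2 + n3 + n4 + n5
- Left out: u, unless that scan replaces a missed scheduled MRI

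**The case against.** The strongest reply is that the ordinary reading is harmless. SAP 4.7 defines baseline variable by variable, so a programmer would compute change for CEL and lesion size and leave the T2 cells blank. A blank row misleads nobody. The new/enlarging count is itself an increase and is summarised at every scheduled visit. All collected data appear in Listing 16.2.5, nine patients are planned, and the DSMB separately receives the numbers of new lesions (Protocol 19.1.3). The analyses are exploratory, without formal hypotheses (Protocol 16.1 and 16.2). The table shells in SAP Appendix 1, which I have not seen, may already restrict the change to CEL.

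Most of this stands. It rules out a stronger inference that a reader might draw: that the table would present worsening as improvement. A hypothetical patient with 2 CELs at Visit 1 and 1 new T2 lesion at the next scan would show 1 − 2 = −1 under the literal rule. That needs a subtraction across two variables, contrary to 4.7, and it is possible only for new/enlarging T2. The adjacent count row would still show the new lesion. No document gives expected CEL counts, and Protocol 5.2.1 does not select for disease activity, so the frequency of such a sign reversal cannot be stated. Nor do the documents support saying that lesion size lacks a baseline.

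The reply does not supply a valid T2 change, and it does not bring unscheduled counts into the summary.

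**Conclusion.** The defect is real and limited. Two of the four promised changes, for new/enlarging T2 and total T2, cannot be validly computed under either baseline in the SAP. The likely product is empty rows; the possible one is a meaningless difference for new/enlarging T2. The SAP text also has no since-baseline summary of new/enlarging T2, and new lesions first seen on an unscheduled scan can be missing from the summary while present in the listing. No data are lost and no error rate is involved. This is a modest correction to the specification of a descriptive primary safety endpoint. It rests on the grid as printed, on the footnote covering unscheduled scans, and on the SAP text without its shells.

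**What to change.** In SAP 5.5.3 and Table 15.2.3:

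- Limit change from baseline to CEL, at the later visits where CEL is collected and against Visit 1 CEL, and to lesion size against its own Visit 1 value, if measured.
- Present total T2 as a baseline characteristic only.
- Keep the new/enlarging T2 counts per interval, labelled as relative to the previous MRI.
- Add, per patient and by dose group, the cumulative number of new/enlarging T2 lesion events since the baseline MRI, including those found at unscheduled scans.

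The cost is a wording change, matching shells and one derived variable from data already collected. The cumulative figure has a drawback: a lesion that enlarges repeatedly can be counted more than once, so it must be labelled as events and not as lesions gained. The SAP Introduction sends changes made after database lock to an addendum. Making this one before lock avoids that.

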5.5.4 Expanded Disability Status Scale

The EDSS is an ordinal scale used for assessing neurological impairment in MS based on a neurological examination. It consists of scores in each of seven functional systems (FSs), as well as ambulation score that are then combined to determine the EDSS steps (ranging from 0 (normal) to 10 (death due to MS)).

EDSS assessment data from eCRF include:

- Visual function score (0 - 6)
- Brainstem functions score (0 - 5)
- Pyramidal functions score (0 - 6)
- Cerebellar functions score (0 - 5)
- Sensory functions score (0 - 6)
- Bowel and bladder functions score (0 - 6)
- Cerebral functions score (0 - 5)
- Ambulation score (0 - 12)
- EDSS score (0 - 10)

The following statistical output will be presented:

Table 15.2.4 Summary of EDSS Score – Modified Safety Analysis Set

EDSS score including change from baseline (last value before first blood donation) at each visit will be summarized by dose group and overall. This summary will be performed by treatment cycle subgroup.

Listing 16.2.6 Expanded Disability Status Scale – Enrolled Analysis Set

EDSS, ambulation score and FS assessment data will be listed.

5.5.5 Nine Hole Peg Test

The 9HPT is a quantitative measure of upper extremity (arm and hand) function. It is composed of a square board with nine pegs. At one end of the board there are holes for the pegs to fit into, and at the other end is a dish to store the pegs. The patient has to pick up each of the nine pegs one at a time and

place them as quickly as possible in the nine holes. Once all pegs are placed in the holes, the patient has to remove them again one at a time as quickly as possible and replace them into the container. The total time to complete the task is recorded. Both the dominant and non-dominant hands are tested twice (two successfully completed trials of the dominant hand, followed immediately by two successfully completed trials of the non-dominant hand). The best result will be recorded in the eCRF.

An increase of 20% in the timing of the 9HPT in any of arms is defined as an indicator for an increase of disease severity. The number and percentage of subjects with a clinically significant change in the timing of 9HPT will be summarized for each (dominant and non-dominant) arm and overall, when the increase is observed in any of arms. If the task was completed at baseline but not completed due to physical limitations at post-baseline assessments, this will also be considered as an increase of disease severity.

The following statistical output will be presented:

Table 15.2.5.1 Summary of 9HPT – Modified Safety Analysis Set

The default summary statistics of 9HPT test score in seconds and relative change from baseline (last value before first blood donation) of 9HPT test results will be presented by dose group and overall. This summary will be performed by treatment cycle subgroup.

Table 15.2.5.2 Summary of Clinically Significant Change in 9HPT – Modified Safety Analysis Set

Number and percentages of patients with a clinically significant change in the time of 9HPT will be presented for dominant, non-dominant arm and overall (for any of arms) by dose group and overall. This summary will be performed by treatment cycle subgroup.

Listing 16.2.7 Nine Hole Peg Test – Enrolled Analysis Set

9HPT assessments and relative change from baseline together with reason of non-completion will be listed.

5.5.6 Timed 25-Foot Walk

The T25FW is a quantitative measure of walking function. The examining investigator will time the patient from the start of the walk to the end of the 25 feet. The task will be immediately administered again by having the patient walk back the same distance. The score for the T25FW will be the average (in seconds) of the two complete trials. In case only one trial is available the score will be equal to the time of available trial.

An increase of 20% in walking time of the T25FW is defined as an indicator for an increase of disease severity. If an assistive device was introduced or the test was failed to complete as compared to the baseline it will be considered as a clinically significant change.

The following statistical output will be presented:

Table 15.2.6.1 Summary of T25FW – Modified Safety Analysis Set

The default summary statistics of T25FW test score in seconds and relative change from baseline of T25FW test results will be presented by dose group and overall. This summary will be performed by treatment cycle subgroup.

Table 15.2.6.2 Summary Clinically Significant Change in T25FW – Modified Safety Analysis Set

Number and percentages of patients with a clinically significant change as defined above will be presented by dose group and overall. In addition, the number and percentage of patients with clinically significant increase in walking time of the T25FW as well as number and percentage of patients for whom assistive device was introduced or who failed to complete the test as compared to the baseline

will be presented by dose group and overall. This summary will be performed by treatment cycle subgroup.

Listing 16.2.8 Timed 25-Foot Walk – Enrolled Analysis Set

T25FW assessments and relative change from baseline (Visit 1) will be listed.

